7. RATIONALE AND BACKGROUND

Myasthenia gravis (MG) is an autoimmune disease caused by immunoglobulin G (IgG) antibodies against postsynaptic antigens at the neuromuscular junction. IgG autoantibodies impair neuromuscular transmission by binding to acetylcholine receptors (AChR), muscle-specific tyrosine kinase (MuSK) or low-density lipoprotein receptor-related protein 4 (LRP4).

From an immunological point of view, approximately 80% of patients with MG have detectable antibodies against AChR. These patients are known as AChR antibody positive.

The estimated prevalence rate for MG is 77.7 per million persons (range 15–179) and the estimated incidence rate is 5.3 per million person-years (range 1.7–21.3) [Carr 2010].

MG occurs in both genders, at all ages, and in all races [Carr 2010, McGrogan 2010]. The most common age of MG onset is between 20 and 40 years. In this age group, about 60% of patients are women. In older age groups, men are affected more often, and the disease is often misdiagnosed. As a result, there is a bimodal distribution with a female predominance in the second to third decade of life and male predominance in the sixth to eighth decade [Philips 2004, Spillane 2012].

MG can be classified into various subgroups based upon antibody status, age of onset and/or degree of muscle involvement. Ocular symptoms are the most common initial presentation of disease and about two thirds of ocular MG patients progress to generalised MG (gMG) within the first 2-3 years (Anil 2020).

A considerable variation exists in the management of gMG, and treatment is not standardized. Current treatment options include acetylcholinesterase (AChE) inhibitors, and long-term immune therapies with immunosuppressive agents such as corticosteroids, azathioprine, cyclosporine, and mycophenolate, but tacrolimus, methotrexate, and cyclophosphamide are also used. There is no consensus on the choice of immunosuppressive agent. Thymectomy is also a treatment option for patients with generalised MG. Monoclonal antibodies such as eculizumab or rituximab are used for more refractory cases [Vyvgart EPAR].

Short term immune therapies such as plasmapheresis/plasma exchange (PLEX) and intravenous immunoglobulins (IVIg) are typically used for treatment of severe exacerbations of gMG [Vyvgart EPAR].

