With the exception of AChE inhibitors, the complement inhibitor eculizumab, and a liquid formulation of azathioprine, which have received regulatory approval in Europe for the treatment of gMG, all other existing therapies are used off-label [Vyvgart EPAR].

In the United States (US), efgartigimod is approved for the indication of gMG in adult patients who are AChR antibody positive and in the EU it is approved as an add-on to standard therapy for the treatment of adult patients who are AChR antibody positive.

The recommended dose of efgartigimod is 10 mg/kg as a 1-hour intravenous infusion to be administered in cycles of once weekly infusions for 4 weeks. Subsequent treatment cycles are administered according to clinical evaluation. The frequency of treatment cycles may vary by patient.

In the EU Risk Management Plan (RMP) for efgartigimod, serious infections, is considered to be an important potential risk. As efgartigimod induces a transient lowering in IgG levels, there is a potential

risk for infections associated with the lowered IgG levels. In the randomized placebo-controlled study of 167 patients ARGX-113-1704, 84 patients with gMG were exposed to efgartigimod and the most frequently observed adverse reactions were upper respiratory infections (10.7% in the efgartigimod patients and 4.8% in the placebo patients) and urinary tract infections (9.5% in the efgartigimod patients and 4.8% in the placebo patients). In the patients who received efgartigimod, these events were \leq Grade 2 according to the Common Terminology Criteria for Adverse Events (CTCAE). Overall, treatment emergent infections were reported in 46.4% of patients treated with efgartigimod and 37.3% of patients treated with placebo. The frequency of infections in the efgartigimod treated patients did not increase with repeated cycles of treatment. There were no serious infections or opportunistic infections in the efgartigimod treated patients. This study will evaluate the occurrence of serious infections in gMG patients treated with efgartigimod in the real world setting under conditions of normal clinical practice compared to gMG patients who are not treated with efgartigimod.

During clinical development of the IV formulation, in the efgartigimod phase 3 placebo-controlled 26 week clinical study, ADAPT, there were 2 reported neoplasm events, 1 (1.2%) in the efgartigimod treatment arm and 1 (1.2%) in the placebo treatment arm.

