9. RESEARCH METHODS

9.1 Study Design

This is a non-interventional, prospective, post authorisation safety study.

Patients with gMG who are expected to start treatment with efgartigimod at enrolment or are within their first cycle of efgartigimod at enrolment will be eligible to enrol into the efgartigimod cohort. Patients with gMG who have not been exposed to efgartigimod and for whom it is not planned to start treatment with efgartigimod at enrolment will be eligible to enrol into the non-efgartigimod cohort. It is anticipated that 340 patients will be enrolled in each cohort.

Patients will be treated and observed according to normal clinical practice. Participation in this study does not limit the physicians` clinical decision making as to the most appropriate treatment for the patient during the course of the study. No visits or investigations outside of normal clinical practice will be required. The enrolled patients will be followed prospectively until end of study participation, loss to follow up, consent withdrawal, or death, whichever comes first. All adverse events (AEs) will be collected throughout the duration of the study.

Enrolment of patients will be over a 5-year period. The follow up of patients will continue for 5 years from the time the last patient has been enrolled. Patients will be followed regardless of whether they continue or discontinue efgartigimod. Assuming a 5-year enrolment period this will allow for a maximum of 10 years of follow-up and a minimum of 5 years. A patient will be considered to be an efgartigimod exposed patient if he/she has received at least one dose of efgartigimod.

In order to minimise heterogeneity between the two cohorts, patients in the efgartigimod cohort will be matched at enrollment with a patient in the non-efgartigimod cohort for the following criteria:

- Age (\pm 5 years)
- Myasthenia Gravis -Activities of Daily Living (MG-ADL) score (0-5, 5-9, and >9) ([Wolfe, 1999](#))
- Region (within EU and within US)

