9.2.1 Selection of Study Population

Patients with gMG who are expected to start treatment with efgartigimod at enrolment or are within their first cycle of efgartigimod at enrolment will be eligible to enrol into the efgartigimod cohort. Patients with gMG who have not been exposed to efgartigimod and for whom it is not planned to start

treatment with efgartigimod at enrolment will be eligible to enrol into the non-efgartigimod cohort.

Physicians participating in the study will be instructed to invite all patients who meet study eligibility criteria to enrol until the enrolment period is closed.

Inclusion Criteria (efgartigimod cohort)

1. Patients diagnosed with gMG who are expected to start commercial efgartigimod at enrolment or who are within their first cycle of efgartigimod at enrolment
2. Have provided appropriate written informed consent

Inclusion Criteria (non-efgartigimod cohort)

3. Patients diagnosed with gMG who have not been exposed to efgartigimod and for whom it is not planned to start treatment with efgartigimod at enrolment
4. Have provided appropriate written informed consent

Exclusion Criteria

None

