9.3 Variables

Electronic case report forms (eCRFs) will be specifically designed for the collection of data from this study. An overview of the categories of study variables (raw data) to be collected for each enrolled patient is summarized in [Table 1](#). There may be some missing data if any assessments are not performed as part of normal clinical practice.

Table 1: Study Variables*

Category	Variables	Baseline	Follow up
Confirmation of eligibility, demographics, study status	
 Date of appropriate informed consent for study enrolment Eligibility assessment Demographic characteristics 	✓	
Past and current medical history	
 Relevant medical history including key co-morbidities (including past history of infections) 	✓	

Category	Variables	Baseline	Follow up
	
 Immune status (immunocompromised or immunocompetent) 	✓	✓
gMG Disease	
 Date of diagnosis 	✓	
	
 Criteria used for diagnosis of gMG 	✓	
	
 Antibody status (AChR, MuSK, anti-LRP4)/date 	✓	
	
 Clinical classification (Myasthenia Gravis Foundation of America recommendations) (Jaretzki, 2000) 	✓	✓
	
 Previous myasthenia crises 	✓	
	
 Thymectomy 
 Date Histology 	✓	✓
	
 MG-ADL questionnaire 	✓	✓
Renal function	
 Estimated glomerular filtration rate (eGFR) 	✓ (Most recent prior to initiation of efgartigimod therapy)	✓
gMG treatments in period from diagnosis prior to enrollment (excluding efgartigimod)	
 Drug name, start and stop dates 
 Acetylcholinesterase inhibitors Corticosteroids Other immunosuppressants (specify) Monoclonal antibodies (specify) Plasmapheresis/plasma exchange acute Plasmapheresis/plasma exchange chronic IVIg therapy acute IVIg therapy chronic Other 	✓	

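### Efgartigimod is approved only for AChR-positive adults, yet comparators may have any antibody status and are not matched on it, so about one in five may have few or no treated counterparts

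*Protocol*

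**What the plan says.** **Label.** Protocol Section 7 states that in the US "efgartigimod is approved for the indication of gMG in adult patients who are AChR antibody positive" and that "in the EU it is approved as an add-on to standard therapy for the treatment of adult patients who are AChR antibody positive". The same section says that "approximately 80% of patients with MG have detectable antibodies against AChR".

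**Eligibility (Section 9.2.1).** The treated cohort is "Patients diagnosed with gMG who are expected to start commercial efgartigimod at enrolment or who are within their first cycle of efgartigimod at enrolment". The comparator cohort is "Patients diagnosed with gMG who have not been exposed to efgartigimod and for whom it is not planned to start" efgartigimod at enrolment. Neither cohort has an antibody criterion, and there are no exclusion criteria.

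**Matching (Section 9.1 and the abstract).** Each efgartigimod patient is matched at enrolment with a comparator on age within 5 years, MG-ADL band and "Region (within EU and within US").

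**Data and models.** Table 1 in Section 9.3 lists "Antibody status (AChR, MuSK, anti-LRP4)/date" at baseline, collected only if available in routine practice. The base models in Section 9.7 contain treatment group and country. Imbalanced baseline measures that are judged to be confounders are added as covariates, or a propensity score is used if there are many. Section 9.9 discusses severity, evolving care and treatment heterogeneity. It does not mention antibody status.

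**The concern.** Because the treated cohort is defined by starting commercial drug, the label makes it AChR-positive except for off-label use. The comparator cohort is drawn from all gMG. The protocol says matching is there to reduce heterogeneity between the cohorts, but it leaves out the one serologic characteristic that defines who can be treated on label.

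Two things are at stake. The first is comparability: part of the comparator cohort may have hardly any treated patients like them. The second is information: if those comparators are later set aside to restore comparability, the comparison rests on fewer patients than Table 4 assumes. Matching is fixed at enrolment, so neither can be repaired in full at the analysis stage.

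**Working it through.** **Inputs from the protocol**
- AChR-positive share of MG patients: 80% (Section 7)
- Enrolled per cohort 340; completers per cohort 270 (Section 9.5)
- Comparator proportion 20%; treated proportion 30% or 31%; two-sided alpha 0.05; normal approximation (Section 9.5, Table 4)

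**Step 1: reproduce the stated power.** With unpooled variance, power = Φ(d/SE − 1.96), where SE = √[p₁(1−p₁)/n₁ + p₂(1−p₂)/n₂].
- 20% v 30%, 270 per arm: SE = √(0.16/270 + 0.21/270) = 0.0370; 0.10/0.0370 = 2.70; power = Φ(0.74) = 77.1%. Table 4 states 77%.
- 20% v 31%, 270 per arm: SE = √(0.16/270 + 0.2139/270) = 0.0372; 0.11/0.0372 = 2.96; power = Φ(1.00) = 84.0%. Table 4 states 84%.

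Using the pooled variance under the null gives 76.7% and 83.7%. The protocol's arithmetic is correct.

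**Step 2: comparators outside the labelled population.** The share is 1 − 0.80 = 0.20.
- Enrolled: 0.20 × 340 = 68
- Completers: 0.20 × 270 = 54, leaving 270 − 54 = 216 AChR-positive

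**Step 3: power if the comparison is restricted afterwards, 216 v 270.** This assumes that all treated completers are AChR-positive, that dropout does not depend on serology, and that AChR-positive comparators have the stated 20% risk.
- 20% v 30%: SE = √(0.16/216 + 0.21/270) = 0.0390; 0.10/0.0390 = 2.57; power = Φ(0.61) = 72.8% unpooled, 71.3% pooled
- 20% v 31%: SE = √(0.16/216 + 0.2139/270) = 0.0392; 0.11/0.0392 = 2.81; power = Φ(0.85) = 80.2% unpooled, 78.9% pooled

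**Step 4: sensitivity to the share.** The 80% is for all MG, so the gMG share is uncertain. If AChR-positive patients are preferentially given efgartigimod, those left for the comparator cohort contain more AChR-negative patients. With a fraction f of AChR-positive patients treated (f is assumed), the share is 0.2/(0.2 + 0.8(1 − f)). This is 25% at f = 0.25 and 33% at f = 0.5.

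| AChR-negative share (assumed except 20%) | Of 340 enrolled | AChR-positive completers | Power, 20% v 30% (pooled) | Power, 20% v 31% (pooled) |
|---|---|---|---|---|
| 10% | 34 | 243 | 74% | 82% |
| 20% | 68 | 216 | 71% | 79% |
| 25% | 85 | 202.5 | 70% | 77% |
| 33% | 113 | 180 | 66% | 74% |

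**Step 5: can Section 9.7 repair it?** The imbalance rule may well bring antibody status into the model. Where there are few or no treated AChR-negative patients, however, a covariate either extrapolates or leaves the AChR-negative comparators contributing almost nothing to the treatment contrast. A propensity score would have to trim or downweight them. Either way the comparison moves towards the restricted one in Step 3.

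**The case against.** **No stated link between serology and outcome.** An unmatched factor biases the comparison only if it predicts the outcome. Section 7 lists gMG treatments without separating them by antibody status, and Section 9.5 gives infection figures for MG overall. A reader might infer that a different serologic mix must shift infection or malignancy risk, and so bias the result or cut power well below the Step 3 figures. The protocol does not support this. Any such figure needs an assumed risk in AChR-negative patients that the protocol does not supply. This objection stands.

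**Overlap may not be absent.** The treated cohort has no antibody criterion, and Section 11.1 makes off-label use a reportable special situation. The number of AChR-negative treated patients is unknown. A reader might infer that there are none, but the supportable wording is few or none.

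**Power does not size this study.** Section 9.5 calls the analysis descriptive and exploratory and bases the size on the precision of the incidence proportion. Table 4 is supporting justification. The precision of the efgartigimod estimate is untouched. If early discontinuers count, as Table 4 allows, the 330 row restricted to 264 comparators keeps about 80–81% power for a 10-point increase (81.0% unpooled, 79.8% pooled). The 300 row, restricted to 240, falls from 81% to about 76–77%.

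**The comparator fits the stated objective.** Section 8 compares treated patients with gMG patients not exposed to efgartigimod and does not require label eligibility. Section 9.9 already concedes selection bias and heterogeneity.

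**Some of this belongs to the SAP.** Overlap checks and trimming may be specified there, so their absence from the protocol is no fault. What remains is that the matching factors are fixed by the protocol at enrolment, and no SAP can supply treated counterparts afterwards.

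**Conclusion.** The point holds as a weakness in comparability and overlap that the protocol builds in at enrolment. About one in five comparators, roughly 68 of 340, may have few or no treated counterparts apart from off-label use. This rests on the protocol's 80% figure for all MG and on treatment mostly following the label.

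The size and direction of any bias are unknown, because the protocol does not relate antibody status to infection or malignancy. The measurable cost is moderate: restricting afterwards to AChR-positive comparators loses about 4 to 6 power points at the 20% share, depending on the variance formula. It should not be read as an error in the sample size, since Table 4 reproduces, nor as evidence that the comparison will mask or exaggerate a risk.

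**What to change.** **Change.** In Section 9.1 and the abstract, add AChR antibody status (positive / not positive or unknown) to the matching factors. In Section 9.7, prespecify the efgartigimod-versus-comparator models in AChR-positive patients of both cohorts alongside the all-patient models, with AChR-negative and unknown patients reported separately.

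**What it achieves.** If the treated cohort is essentially AChR-positive, 340 matched comparators will be too, and the power in Table 4 is kept without enlarging the study. Without matching or an antibody criterion, obtaining 340 AChR-positive comparators at an 80% share would take about 340/0.80 = 425.

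**Cost.** Protocol and SAP wording only, with no new assessment, since antibody status is already a baseline variable. The pool of candidate comparators becomes somewhat smaller, and a fourth matching factor is added in a rare disease. Patients without a recorded antibody result fall in a separate stratum. The change does most good if made before enrolment is far advanced.

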9.2.2 Study Procedures

Patient care will follow the normal treatment practices in the respective country and at the specific site. All patients in the study will receive care according to usual clinical practice, and clinical care will not be mandated by the protocol. No additional visits or investigations will be performed beyond usual clinical practice. The choice of ongoing medical treatment for the duration of the study will be made independently by the physician in the regular course of practice and will not be influenced by participation in this study.

Patient enrolment will be over a 5-year period. The follow-up of patients will continue for 5-years from the time the last patient has been enrolled. Patients will be followed regardless of whether they continue or discontinue efgartigimod. Thus, patients enrolled at the beginning of the study may be followed for a maximum period of 10-years.

Efgartigimod or any other treatment will not be provided by or paid for by argenx. Assessments are as per standard of care and will not be provided by or paid for by argenx.

9.2.3 Schedule of Assessments

No mandatory visits, tests, or assessments are required for this study. All visits will be scheduled and conducted according to the clinical site's normal clinical practice. Data will be extracted by the site from the medical record and entered via a secure web-based Electronic Data Capture (EDC) system following clinic visits. Patients will be provided with regular reminders to notify sites of AEs in between clinic visits. AEs should be reported in accordance with the requirements in Section 11.

The Clinical Research Associate (CRA)/monitor will monitor whether data entry is occurring and, if needed, conduct contact calls with the sites to ensure sites are remaining compliant to the requirements of the study and that adequate follow-up and contact is being made by the site with their patients.

9.2.4 Participation Strategies

Every effort will be made to ensure adequate follow-up and ongoing contact with patients.

The consenting patient/legal guardian will complete a patient/legal guardian contact form (including physical address, mailing address, phone number, and e-mail address) and will also be asked to identify one or more secondary contacts such as the patient’s primary care physician and one or more other persons. This information will remain at the site and will not be entered into the study database. This information will be used by the site to provide the patient/legal guardian with study update materials and/or current information as it becomes available. This information will also be used to minimise loss to follow-up.

In the event a physician retires, or discontinues participation from the study, a transition plan will be put in place to enable continuing participation by the patient. In the event a patient moves to a new location or chooses to leave their current physician or treatment center, patients/legal guardians will be provided with information as to how to locate a participating physician in their area or how to provide the study information to a new physician who may not be participating yet.

The goal of these strategies is to enhance patient retention, potentially resulting in a lower drop-out rate and improved quality of data. Over the course of a long-term study, patients may become lost to follow-up due to medical or social reasons.

9.2.5 Loss to Follow-up

If there has been no data entered by the site for an enrolled patient within 6 months of the last data entry time point, the study management team will contact the site to confirm the patient’s status and whether the patient is still under the Healthcare Professional’s (HCP) care. If the patient is still participating in the study, the study management team will remind the site that data must be entered into the EDC at least within 3 months of new data for each enrolled patient and will confirm with the site when the data will be entered. If the patient is no longer being treated by this HCP, the study management team will attempt to identify and obtain any new HCP information and will establish contact with the new HCP to ensure the patient’s data continues to be collected in the study. If the patient has not reported any data to the site or the site has not been able to contact the patient/or secondary contacts to obtain patient status for at least 12 months then a patient will be considered lost to follow-up.

9.3 Variables

Electronic case report forms (eCRFs) will be specifically designed for the collection of data from this study. An overview of the categories of study variables (raw data) to be collected for each enrolled patient is summarized in [Table 1](#). There may be some missing data if any assessments are not performed as part of normal clinical practice.

Table 1: Study Variables*

Category	Variables	Baseline	Follow up
Confirmation of eligibility, demographics, study status	
 Date of appropriate informed consent for study enrolment Eligibility assessment Demographic characteristics 	✓	
Past and current medical history	
 Relevant medical history including key co-morbidities (including past history of infections) 	✓	

Category	Variables	Baseline	Follow up
	
 Immune status (immunocompromised or immunocompetent) 	✓	✓
gMG Disease	
 Date of diagnosis 	✓	
	
 Criteria used for diagnosis of gMG 	✓	
	
 Antibody status (AChR, MuSK, anti-LRP4)/date 	✓	
	
 Clinical classification (Myasthenia Gravis Foundation of America recommendations) (Jaretzki, 2000) 	✓	✓
	
 Previous myasthenia crises 	✓	
	
 Thymectomy 
 Date Histology 	✓	✓
	
 MG-ADL questionnaire 	✓	✓
Renal function	
 Estimated glomerular filtration rate (eGFR) 	✓ (Most recent prior to initiation of efgartigimod therapy)	✓
gMG treatments in period from diagnosis prior to enrollment (excluding efgartigimod)	
 Drug name, start and stop dates 
 Acetylcholinesterase inhibitors Corticosteroids Other immunosuppressants (specify) Monoclonal antibodies (specify) Plasmapheresis/plasma exchange acute Plasmapheresis/plasma exchange chronic IVIg therapy acute IVIg therapy chronic Other 	✓	
gMG treatments at or following enrollment (excluding efgartigimod)	
 Drug name, dose, start and stop dates 
 Acetylcholinesterase inhibitors Corticosteroids Other Immunosuppressants (specify) Monoclonal antibodies (specify) Plasmapheresis/plasma exchange acute Plasmapheresis/plasma exchange chronic IVIg therapy acute IVIg therapy chronic Other 	✓	✓

Category	Variables	Baseline	Follow up
Efgartigimod treatment	
 • Date of administration • Reason for interruption during cycle of treatment • Reason for permanent discontinuation whilst on study 	✓	✓
Other comedications at or following enrollment for conditions other than gMG	
 • Drug name, start and stop dates • Indication 	✓	✓
Live/attenuated vaccinations 2 months prior to enrollment to 2 months after last Vyvgart dose	
 • Live/attenuated vaccine 
 ○ Vaccine ○ Date 	✓	✓
Adverse Events (AEs)/Serious Adverse Events (SAEs)	
 • AEs, SAEs 		✓
Events of interest	See Table 2		✓

*All variables will be collected ONLY if available as part of routine clinical practice

A patient will be considered to be an efgartigimod exposed patient if he/she has received at least one dose of efgartigimod.

Additionally, taking into account the variable follow up time and time interval between cycles, the following will be measured for efgartigimod:

- Number of administrations per year
- Total duration of the exposure
- Total number of administrations

The exposure time window of efgartigimod is 56 days +/-3 days after the last dose.

Events of interest in this study will be pre-specified as per [Table 2](#) below.

Table 2: Pre-specified events of interest

Event of interest	Definition	Measurement
Serious infection	Any serious adverse event coded to the Medical Dictionary for Regulatory Activities (MedDRA) System Organ Class (SOC) of Infection and Infestation. See Section 11 for definition of Serious.	Proportion of patients who report serious infections during the course of the study in the efgartigimod treated cohort compared to the non-efgartigimod cohort. Incidence rate of serious infections per patient-years exposed in the efgartigimod treated cohort compared to the non-efgartigimod cohort.
Malignancy	Any adverse event (AE) within the Standardised MedDRA Query (SMQ) Malignancies (Narrow) .	Proportion of patients who report events of malignancy during the course of the study in the efgartigimod treated cohort compared to the non-efgartigimod cohort. Incidence rate of events of malignancy per patient-years exposed in the efgartigimod treated cohort compared to the non-efgartigimod cohort.
Adverse event (AE)	Any untoward medical occurrence in a patient administered a pharmaceutical product or device and that does not necessarily have a causal relationship between the product and the event. An AE can, therefore, be any unfavorable or unintended sign (including an abnormal laboratory finding) or symptom temporally associated with a medicinal product, whether or not related to the medicinal product.	Proportion of patients who report AEs during the course of the study in the efgartigimod treated cohort compared to the non-efgartigimod cohort. Incidence rate of AEs per patient-years exposed in the efgartigimod treated cohort compared to the non-efgartigimod cohort.
Serious adverse event (SAE)	As per definition in Section 11.	Proportion of patients who report SAEs during the course of the study in the efgartigimod treated cohort compared to the non-efgartigimod cohort. Incidence rate of SAEs per patient-years exposed in the efgartigimod treated cohort compared to the non-efgartigimod cohort.

AEs (serious and non-serious) in immunocompromised patients
	
Immunocompromised definition (moderate or severe) based upon Centre for Disease Prevention (CDC) People Who Are Immunocompromised CDC.
	
Proportion of AEs/SAEs reported in immunocompromised patients and immunocompetent patients in the efgartigimod cohort.
 
Incidence rate of AEs/SAEs per patient-years exposed in immunocompromised patients and immunocompetent patients in the efgartigimod cohort.


AEs (serious and non-serious) in patients treated with monoclonal antibodies
	
Patients receiving monoclonal antibodies other than FcRn (e.g., adalimumab, tocilizumab, ixekizumab, rituximab) within 6 months prior to efgartigimod administration.
	
Proportion of AEs/SAEs reported in patients treated with monoclonal antibodies vs patients not treated with monoclonal antibodies in the efgartigimod cohort.
 
Incidence rate of AEs/SAEs per patient-years exposed in patients treated with monoclonal antibodies vs patients not treated with monoclonal antibodies in the efgartigimod cohort.

AEs (serious and non-serious) in patients treated with live attenuated vaccine
	
Patients receiving live/attenuated vaccine (e.g., live-attenuated flu vaccine, measles, mumps and rubella, polio, smallpox, chickenpox, yellow fever, Japanese encephalitis, shingles, rotavirus) in the period of 4 weeks prior to or 2 weeks after efgartigimod administration.
	
Proportion of AEs/SAEs reported in patients who have received live/attenuated vaccine vs patients who have not received live/attenuated vaccine in the efgartigimod cohort.
 
Incidence rate of AEs/SAEs per patient-years exposed in patients who have received live/attenuated vaccine vs patients who have not received live/attenuated vaccine in the efgartigimod cohort.

AEs (serious and non-serious) in patients with moderate to severe renal impairment
	
Moderate renal impairment: eGFR 30-59 mL/min/1.73 m² Severe renal impairment: eGFR < 30 mL/min/1.73 m²
	
Proportion of AEs/SAEs reported in patients with moderate renal impairment vs patients who have normal renal function in the efgartigimod cohort.
 
Incidence rate of AEs/SAEs per patient-years exposed in patients with moderate renal impairment vs patients who have normal renal function in the efgartigimod cohort.
 
Proportion of AEs/SAEs reported in patients with severe renal impairment vs patients who have normal renal function in the efgartigimod cohort.

		Incidence rate of AEs/SAEs per patient-years exposed in patients with severe renal impairment vs patients who have normal renal function in the efgartigimod cohort.
--	--	--

